13.9 Overall Type 1 Error Control

The overall Type I error is two-sided 5%. No interim analyses are planned.

A hierarchical testing plan is in place to control Type I error to extend labeling claims in the following pre-defined testing order where statistical significance (two-sided $p < 0.05$) is required at each step:

1. Primary: K/N will delay time to relapse relative to K/L and K/P
2. Secondary: K/N will separate from K/L and K/P by 72 hours, with sustained difference between groups thereafter

3. Secondary: All-cause discontinuation (including discontinuation for continued suicidal ideation) will be lower in K/N than K/L and K/P.
4. Secondary: K/N will separate from K/L and K/P starting at Day 7, with sustained difference thereafter
5. Secondary: Improvements within the K/N group observed at Week 2 will remain stable to end of study.

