8.1.1 Study Visits and Assessments

A schedule of study visits and assessments is provided in Table 3 Schedule of Study ActivitiesTable 3

Table 3 **Schedule of Study Activities**

Assessment/Activity	Study Day	Screening Period 48 hrs	Stage 1			Stage 2										Follow Up /ET Day 70
			Ket. Dosing	4 hr	10 hr +2 hours	Day 1	Day 6	Day 7	Day 10	Day 14	Day 21	Day 28	Day 35	Day 42		
						24 hr post dose	+/- 1 day									
Visit Name/No.	Screen	Baseline			1	2	3	4	5	6	7	8	9	10		
Informed Consent		X														
MINI 7.0.2 DSM 5		X														
Demographics		X														
Medical History		X														
Psychiatric History		X														
Physical Exam		X								X				X		
Vital Signs		X	X	X		X		X	X	X	X	X	X	X		
ECG		X				X				X				X		
Concomitant Medications		X	X				X	X	X	X	X	X	X	X		
C-SSRS		X	X	X	X	X	X	X	X	X	X	X	X	X		
Phone Visit*					X		X									
Adverse Events		X	X	X	X	X	X	X	X	X	X	X	X	X		
CHRT—C, SR		X						X		X	X	X	X			
Remote Independent Rater Interview		X**														
CADSS			X	X												
BISS		X	X	X		X		X	X	X	X	X	X	X		
SIBQ			X	X		X		X	X	X	X	X	X	X		
Blood Draw for drug analyses		X				X***				X***				X***		
BARS			X					X	X	X	X	X	X	X		
BPRS			X	X												
PRISE			X	X		X		X	X	X	X	X	X	X		
Chemistry, CBC		X								X				X		
Urine Tox Screen		X								X				X		
Pregnancy Test (Urine)		X								X				X		
Ketamine Infusion			X													
Randomization						X										
Drug Dispensation & Pill Count						X		X		X	X	X	X	X		

*This phone visit should be performed by the site Principal Investigator, or Sub-Investigator. **The independent interview is performed remotely by telephone by independent raters.

***Blood draws for drug analyses 2 hours after the initial dose, prior to administration of NRX-101 on days 14 and 42, and 2 hours after administration of NRX-101 on day 42.

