8.1.6 Randomization

Subjects will be assessed in person 24 hours post-infusion for response to ketamine. Those who do not respond will be provided standard of care for ongoing suicidal ideation. Following the documented observance of a therapeutic response to intravenous ketamine as defined by a 25% or greater reduction in the on the MADRS subset of the BISS score and a score of ≤ 3 on the C-SSRS at 24 hours post infusion, subjects will be randomized 2:1:1 to either a fixed dose combination of experimental drug NRX-101 (DCS + lurasidone), or to an identical capsule containing placebo + lurasidone, or to an identical capsule containing placebo. Randomization blocks will be allocated at the site level to ensure that treatment and control groups are balanced per site. An Interactive Web Response System will be used.

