8.2.6.1 Efficacy Measures

Bipolar Inventory of Symptom Scale (BISS) (Bowden et al., 2007): The BISS is a 44-item clinician-rated scale (22 items for the depression subscale and 22 items for the mania scale), in which each item is rated on a 0-4 severity scale which is which operationally defines each item, confining the assessment to only one behavioral construct. Items are grouped into 10 established symptom clusters, based on prior studies of phenomenology and reports of symptom clusters and principal components in ratings of BD. The timeframe for the BISS is the past 7 days. The BISS scale has been found to have high internal consistency (Chronbach's alpha=0.93 for the Total Scale, 0.92 for the depression subscale, and 0.90 for the mania subscale) and inter-rater reliability (ICC=0.96 for total scale, 0.98 for depression subscale, and 0.95 for mania subscale) (Gonzalez, et al, 2008). Regarding discriminant validity, the BISS total score was able to significantly distinguish between patients in a depressed, manic or mixed episode from subsyndromal patients, recovered patients, and healthy controls (Gonzalez et al, 2008). Convergent validity was demonstrated by strong Pearson correlations (i.e., $r=.64$ to $.94$) between the BISS total score and the BISS depression subscale and the MADRS, and between the BISS total score and the mania subscale and the YMRS across all patient and control groups described above; divergent validity was demonstrated by smaller and (i.e., $r=-.14$ - 0.30) correlations between the BISS depression subscale and the YMRS scale, and between the BISS mania scale and the MADRS ($r=-.06$ - $.31$).

The Columbia Suicide Severity Rating Scale (C-SSRS) (Posner et al., 2007): The C-SSRS is a low-burden measure of the spectrum of suicidal ideation and behavior that was developed in the National Institute of Mental Health Treatment of Adolescent Suicide Attempters Study to assess severity and track suicidal events through any treatment. It is a clinical interview providing a summary of both ideation and behavior that can be administered during any evaluation or risk assessment to identify the level and type of suicidality present. The C-SSRS can also be used during treatment to monitor for clinical worsening. The C-SSRS will be performed to assess suicidal ideation and behavior. C-CASA is the retrospective counterpart of the more detailed

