11. ASSESSMENT OF EFFICACY

The primary outcome measure will be time to relapse, defined as a return to a score of ≥ 4 on the C-SSRS, and/or a score of 20 on the MADRS subset of the BISS. The RAC will adjudicate each site reported instance of relapse for compliance the protocol definition of time to relapse.

Relapse is a time-to-event outcome reflective of this multi-component disorder. Time to relapse is more sensitive measure than an assessment at a fixed time. Time to relapse will be displayed using a Kaplan-Meier lifetable with the treatment groups compared using a two-sided Wilcoxon-Gehan test and a proportional hazard model to include the above cited covariates.

Titration of DCS or lurasidone within the dosing range will not be considered to be a relapse.

All of the instruments used to measure ASIB or depression constitute serial continuous and ordinal outcomes which will be analyzed using MMRM, which accounts for missing data and early discontinuations. These instruments include the following:

- C-SSRS (and the retrospective C-CASA component)
- CHRT (CHRT-SR and CHRT-C)
- BISS
- SIBQ
- BPRS

The models will include treatment group, study visit, the interaction between study visit and treatment group, the baseline of the variable being analyzed, C-SSRS 24 hours post infusion (1, 2), age (<25 yrs, 25-39 yrs, >40 yrs), and gender as fixed effects. The reason for missing data will be evaluated as a condition of MMRM analysis.

Means, mean changes, standard deviations, and ranges will be presented separately for Stage 1 and then for each Stage 2 treatment group over time. These endpoints will be evaluated within the three study treatment groups for the change from Stage 1 and Stage 2 baselines using a paired t-test and between study treatment groups using an unpaired t-test at each time; these p-values will be presented as descriptive statistics.

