13.3 Study Populations

The study will have prospectively defined study populations including separate evaluability rules for the Ketamine treatment (Stage 1) and randomized treatment (Stage 2).

For Stage 1, the Intent-to-Treat population will include all subjects who received the Ketamine infusion and they have the 24 hours post-infusion efficacy assessments. The Per-Protocol population will include the subset of ITT subjects who were eligible, who had the 24 hour post-infusion efficacy assessments within 18 to 30 hours post the start of the initial infusion, and who had no major protocol violations. The Safety Population will include all subjects treated with Ketamine and with any post-baseline safety data.

For Stage 2, the Intent-to-Treat population will include all subjects who received the randomized study treatment and have any post-baseline efficacy assessments. The Per-Protocol population will include the subset of ITT subjects who were eligible, who have any post-baseline efficacy assessments within 1 day of scheduled visits through Day 7 and within 3 days of scheduled visits through Day 42, and who had no major protocol violations. The Safety Population will include all subjects as treated with study treatment and with any post-baseline safety data.

The ITT population will be used for the primary analyses. If <5% are to be excluded from the ITT population, then the analysis will not be performed for the PP population.

Every effort will be made to encourage patients to comply with the procedures and the assessments involved in study. Non-compliance will be tracked. Protocol violations will be reviewed in real time; prospective rules will be set for exclusions from the PP population.

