Table 12 Time to Relapse: K/N and K/L Groups Followed for 6 Weeks

	90% Power	Reaching Significance
Test significance level, α	0.05	0.05
1 or 2 sided test?	2	2
K/L relapse-free % p_1 at Week 6	30%	30%
K/N relapse-free % p_2 at Week 6	52%	70%
Hazard ratio, $h=\ln(p_1) / \ln(p_2)$	1.841	3.376
Power (%)	90	N/A
Total N	112	112
Total N of relapses required, R	48	62
Total N accounting for 8% Stage 2 losses	124	124
Total N accounting for 30% K non-responders	177	177
Total N accounting for 8% Stage 1 losses	192	192

The secondary efficacy hypotheses will also be evaluated using a hierarchical testing strategy where testing to support labeling claims continues as long as two-sided $p=0.05$ is reached. The first such hypothesis to be tested for the depression endpoints is whether K/N separates from K/L and K/P by 72 hours, with sustained difference between groups thereafter (see **Error! Reference source not found.**). There will be 90% power and two-sided 5% Type I error to detect a 0.754 effect size for the comparison of the K/N against the K/L and K/P treatment groups.

Table 13 Two Group T-test: Equal Effect Sizes

	90% Power	Reaching Significance
Test significance level, α	0.05	$p=0.05$
1 or 2 sided test?	2	2
Effect size, $\delta = \mu_1 - \mu_2 / \sigma$	0.754	0.456
Power (%)	90	N/A
Total N	112	112

Next, all-cause discontinuation (including discontinuation for continued suicidal ideation) will be tested. The hypothesis is that the percent discontinued prior to Week 6 will be lower in K/N than K/L and K/P using a lifetable approach (see **Error! Reference source not found.**).

Table 14 Two Group Log Rank Test: Time to All-cause Discontinuation

	90% Power	Reaching Significance
Test significance level, α	0.05	0.05
1 or 2 sided test?	2	2
K/L success rate p_1 at Week 6	0.225	0.225
K/N success rate p_2 at Week 6	0.6	0.43
Hazard ratio, $h = \ln(p_1) / \ln(p_2)$	3.89	1.77
Power (%)	90	N/A
Total N	112	112
Total # discontinued required, D	60	72

The next hypothesis to be tested is whether K/N will separate from K/L and K/P starting at Day 7, with sustained difference thereafter (see **Error! Reference source not found.**).

The next hypothesis to be tested is whether improvements within the K/N group observed at Week 2 will remain stable to end of study (see **Error! Reference source not found.**).

Table 15 One Group t-test: No Mean Change

	1	2	3	4
Test significance level, α	0.050	0.050	0.050	0.050
1 or 2 sided test?	2	2	2	2

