13.10.4 General Methodology

Time to event analyses will be performed using a Kaplan-Meier lifetable, two-sided Wilcoxon-Gehan test, and proportional hazard models (PHREG) including the following covariates: study treatment, C-SSRS 24 hours post infusion (1,2, or 3), age (<25, 25-39, >40), and gender. The proportional hazard model results for the Intention-to-treat (ITT) population will be considered to be the primary analysis for the primary efficacy endpoint while the MMRM results for the ITT population will be considered to be the primary analysis for the secondary efficacy endpoints.

All of the instruments used to measure ASIB or depression constitute serial continuous and ordinal outcomes which will be analyzed using Mixed-Effect Model Repeated Measure (MMRM) to account for missing data and early discontinuations. The models will include treatment group, study visit, the interaction between study visit and treatment group, the baseline of the variable being analyzed, C-SSRS 24 hours post infusion (1, 2, or 3), age (<25, 25-39, >40), and gender as fixed effects. The reason for missing data will be evaluated as a condition of MMRM analysis.

An autoregressive (AR1) variance covariance structure will be assumed for this analysis. To account for mis-specification of the covariance structure, the Liang and Zeger’s “sandwich” estimator (via the EMPIRICAL option in SAS PROC MIXED) will be used. Restricted maximum likelihood (REML) will be used to estimate all parameters and will be the basis for all hypothesis testing (SAS default). For the primary model including the interaction term, the hypothesis test to perform on the fixed effects will be Type III (SAS® option htype = 3). SAS® PROC MIXED will be used.

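### The second step of the testing hierarchy, separation on depression by 72 hours, has no scheduled rating behind it and so blocks every later secondary claim

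*Combined protocol and SAP*

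**What the plan says.** Section 13.9 sets out a hierarchy to support labelling claims, with two-sided p<0.05 needed at each step. Step 1 is the primary endpoint. Step 2 is "Secondary: K/N will separate from K/L and K/P by 72 hours, with sustained difference between groups thereafter". Steps 3 to 5 are all-cause discontinuation, separation from Day 7, and stability of the Week 2 improvement in the K/N arm.

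Section 13.9 names no endpoint for step 2, but section 13.8.3 does: "The first such hypothesis to be tested for the depression endpoints is whether K/N separates from K/L and K/P by 72 hours". Table 13 gives that comparison 90% power at an effect size of 0.754. Section 13.8.3 also places a C-SSRS hypothesis last, after the five steps of 13.9.

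On the data, section 8.1.1 states: "A schedule of study visits and assessments is provided in Table 3". Section 13.5.2 ties the secondary measures to the times in that table. Section 8.1.6 says: "Subjects will be assessed in person 24 hours post-infusion for response to ketamine". That assessment decides who is randomised.

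On the analysis, section 11 says: "All of the instruments used to measure ASIB or depression constitute serial continuous and ordinal outcomes which will be analyzed using MMRM". Section 13.10.4 makes the MMRM the primary analysis for the secondary endpoints and specifies it so: "The models will include treatment group, study visit, the interaction between study visit and treatment group, the baseline of the variable being analyzed".

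**The concern.** A gate in a fixed sequence needs data that can produce a p-value. Step 2 asks about depression by 72 hours, yet Table 3 has no column between Day 1 and Day 6. If no rating exists in that interval, the step cannot be passed however well the drug works. Because significance is required at every step, formal testing then stops after the primary endpoint. What is at stake is the set of secondary labelling claims that the hierarchy was written to support.

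**Working it through.** **1. The plan's own figure.** Inputs: 56 v 28 evaluable subjects (13.8.3), effect size 0.754, two-sided alpha 0.05 (Table 13). For a pooled t-test the noncentrality is d/√(1/n₁+1/n₂) = 0.754/√(1/56+1/28) = 3.258 on 82 df, with critical value 1.989.
- Exact power is 89.6%.
- The normal approximation gives 90.3%.

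Table 13 therefore reproduces as a per-comparison figure. The arithmetic is sound; what is missing is the data.

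**2. When depression is rated.** The section 11 efficacy instruments are the C-SSRS, CHRT, BISS, SIBQ and BPRS. Only the BISS, with its MADRS subset, is a depression scale. Table 3 marks it at Screen, Baseline, 4 h and Day 1 (24 h), then on Days 7, 10, 14, 21, 28, 35 and 42. It is not marked at 10 h or Day 6. The 24-hour rating determines randomisation, so it precedes study drug.

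**3. Distance from 72 hours.** Table 3 carries a window of plus or minus one day, and the per-protocol rule in 13.3 uses the same tolerance: "who have any post-baseline efficacy assessments within 1 day of scheduled visits through Day 7".

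| | Counted from infusion | Counted from Day 1 dose |
|---|---|---|
| 72-hour mark, hours after infusion | 72 (Day 3) | 96 (Day 4) |
| First post-drug BISS, nominal (Day 7), hours after infusion | 168 | 168 |
| Earliest with window (Day 6), hours after infusion | 144 | 144 |
| Minimum gap after the mark | 144 − 72 = 72 h | 144 − 96 = 48 h |

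There are zero scheduled post-drug BISS ratings by 72 hours on either time origin. Reading another scale into step 2 does not help. The first post-drug C-SSRS is at Day 6, the first CHRT and SIBQ at Day 7, and the BPRS stops at 4 h. The finding does not depend on cell alignment in the table, because no Day 2 to Day 5 column exists.

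**4. Whether the model can supply it.** Study visit is a factor in the MMRM and interacts with treatment. The model estimates treatment differences at scheduled visits and does not interpolate to a time with no visit.

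**5. Whether Day 7 can stand in.** Day 7 separation is already step 4, so step 2 would become redundant. Section 8.2.6.1 also says: "The timeframe for the BISS is the past 7 days". A Day 7 score therefore reaches back to about the infusion and does not isolate 72 hours.

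**6. Power if Table 13 is moved to Day 7.** The documents do not give relapse timing by Day 7, so this is an assumption and is shown as a range. Relapsers are withdrawn (8.1), and one withdrawn before Day 7 has no scheduled post-drug BISS. The six-week relapse rates are 30% and 70% (13.8.3).
- No relapse before Day 7: 56 v 28, power 89.6%.
- Constant hazard: relapse-free at Day 7 is 0.70^(1/6) = 0.942 and 0.30^(1/6) = 0.818. This leaves 56 × 0.942 = 52.8 and 28 × 0.818 = 22.9. At 53 v 23, power is 84.6%.
- Half of the six-week relapses before Day 7 (15% and 35%): 56 × 0.85 = 47.6 and 28 × 0.65 = 18.2. At 48 v 18, power is 76.6%.

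The t-test stands in for the MMRM here.

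**The case against.** Nobody disputes that the schedule lacks a 72-hour rating. The objections concern the consequence, the power figures and the remedy.

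- **First-week contacts.** Section 8.1 plans twice-daily contact for a week after discharge, partly to collect efficacy data, and 8.2.5.2.3 plans daily contact to assess symptoms. Neither names a scale, so they supply no BISS. They do show that a rating could have been fitted in.
- **Blocked claims may be over-counted.** The C-SSRS hypothesis is not in the 13.9 list. Step 5 claims stability, yet Table 15 powers a test of no mean change, where p<0.05 would show change. Both may have flaws of their own, but as written both still sit behind step 2.
- **The Day 7 power figures are pessimistic.** They start from 56 v 28, which already removes the whole 8% Stage 2 loss, and then remove relapsers. Starting from the randomised 62 v 31, constant hazard leaves about 58 v 25 (87.6%), and the half-early assumption about 53 v 20 (80.9%). These are upper bounds. A relapse declared on the MADRS subset would also produce an unscheduled BISS. This objection stands, but neither the defect nor the fix rests on these figures.
- **Other remedies exist.** A 72-hour rating could be added, with a recall period that suits, or the step could be moved to the end. Either would unblock the later steps. That does not make deletion unsound.
- **A separate SAP could settle it.** It could define the score and the time origin, but it cannot create ratings that were not taken.

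**Conclusion.** The concern holds and should be fixed. Step 2 has no scheduled observations: the first post-drug depression rating falls at least 72 hours after the mark counted from infusion, or at least 48 hours after it counted from the first dose. As the sequence is written, three later steps in 13.9 and the last hypothesis in 13.8.3 cannot be formally reached.

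The damage is confined to secondary labelling claims. The primary analysis is untouched, and secondary effects can still be estimated and reported without a formal claim. The conclusion needs only the Table 3 visit days, the fact that the 24-hour rating precedes study drug, and the rule of p<0.05 at each step. Only the Day 7 power range depends on assumed relapse timing.

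**What to change.** Before unblinding:

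1. Delete the 72-hour hypothesis from 5.2, 13.4.2, 13.8.3 and 13.9. Keep the remaining secondary steps in their present order: all-cause discontinuation, Day 7 separation, Week 2 stability.
2. Define the Day 7 step as one contrast: the MMRM difference in the MADRS subset of the BISS at Day 7, K/N versus each comparator. State whether both comparisons must reach p<0.05.
3. Take the requirement of a sustained later difference out of the formal test and report Days 10 to 42 descriptively.
4. If the Table 13 power is kept, attach it to the Day 7 contrast as a per-comparison figure, conditional on 56 v 28 subjects being rated at Day 7.

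The cost is protocol and SAP wording, with no new visit or rating. The 72-hour claim, which the schedule cannot test, is given up, and the earliest formal depression claim moves to Day 7.

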9.5 Dose Adjustment and Stopping Rules

Subjects will be allowed to titrate up or down, as outlined above, in the event of intolerable side effects. No other dose modifications will be allowed.

Every effort will be made to keep the subject in the study for the full study period consisting of 7 days of acute treatment plus 6 weekly follow-up assessments (Days 10, 14, 21, 28, 35, and 42). Acceptable reasons for early discontinuation include the following: 1) non-response to ketamine treatment, 2) request of subject, 3) decision of physician, 4) SAE, 5) and protocol violation.

A subject who decides to discontinue the investigational product will always be asked about the reason(s) and the presence of any AEs. If possible, they will be seen and assessed by an investigator. Adverse events will be followed up (see Section 12.6) until resolution.

If a subject discontinues from the study before randomization to Stage 2, then no further follow-up will be expected. However, if the subject discontinues after randomization, to Stage 2 but before receiving any study treatment, the subject will be asked to return for a final study visit, during which the procedures outlined in the Early Termination Visit procedures will be completed, including AEs and concomitant medication assessments.

If a subject discontinues from the study before completion of Stage 2 and has received at least 1 dose of study drug, the subject will be asked to return for a final study visit, at which the procedures outlined in the Early Termination Visit will be completed. Every effort will be made to follow up with subjects who discontinue from the study prior to Visit 10 (Day 42). If subjects refuse to return to the clinic for the study-related assessments, a modified follow-up through, for example, regular telephone contact or a contact at study closure will be arranged, if agreed to by the subject and in compliance with local data privacy laws/practices. If the subject refuses follow-up, the reason for the refusal and last contact date will be documented in the eCRF and source documents.

Subjects who discontinue from the study will not be replaced.

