13.10.3 Conventions

Means, mean changes, standard deviations, and ranges will be presented separately for Stage 1 and then for each Stage 2 treatment group over time. These endpoints will be evaluated within the three study treatment groups for the change from Stage 1 and Stage 2 baselines using a paired t-test and between study treatment groups using an unpaired t-test at each time; these p-values will be presented as descriptive statistics.

For continuous variables, the mean, standard deviation, minimum, median and maximum will be presented, together with the total number of observations and the number of missing and non-missing values. Unless otherwise specified minimum and maximum values will be reported to the same number of decimal places as the recorded measurements, mean and median are reported to one more decimal place and standard deviation one additional decimal place more than the mean.

For ordinal and categorical variables, absolute and relative frequencies will be reported. Relative frequencies will be based on all observations and reported as percentages to one decimal place. Unless otherwise specified percentages will be based on the number of subjects with data and will not be calculated for missing categories.

Adverse events, medical histories and concomitant medications will be reported on a subject and an event basis. The percentages will be calculated using the number of subjects in the population Analysis Set as the denominator.

All hypotheses will be tested at 5% (final analysis) level of significance using a two-sided test unless otherwise specified.

P-values will be rounded to four decimal places. If a p-value is less than 0.0001 it will be reported as “<0.0001.” If a p-value is greater than 0.9999 it will be reported as “>0.9999”.

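### Step 5 of the testing hierarchy claims stability, but the only test placed under it has a null of no mean change and no margin is stated, so p<0.05 does not show that the improvement held

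*Combined protocol and SAP*

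**What the plan says.** Section 13.9 sets up a fixed sequence: "A hierarchical testing plan is in place to control Type I error to extend labeling claims in the following pre-defined testing order". Each step must be significant at two-sided p<0.05. The fifth and last step is "Secondary: Improvements within the K/N group observed at Week 2 will remain stable to end of study".

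Section 13.8.3 introduces the same hypothesis ("The next hypothesis to be tested is whether improvements within the K/N group observed at Week 2 will remain stable to end of study") and follows it directly with Table 15, titled "One Group t-test: No Mean Change". That table uses two-sided alpha 0.05 and gives standardised changes detectable with 90% or 50% power at N=56 and N=28. The cross-reference in the text is broken, so the link between hypothesis and table is by position.

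Two other sections bear on the test. Section 13.10.3 describes within-group comparisons "for the change from Stage 1 and Stage 2 baselines using a paired t-test" and calls those p-values descriptive. Section 13.10.4 states that "the MMRM results for the ITT population will be considered to be the primary analysis for the secondary efficacy endpoints", but gives no contrast for this hypothesis.

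The plan names no instrument, model contrast, direction or margin for step 5. The end of study is not tied to a visit either. Section 9.5 describes a "full study period consisting of 7 days of acute treatment plus 6 weekly follow-up assessments", the last on Day 42. The hypothesis about the four weeks after treatment is separate (13.4.2), which also points to Day 42.

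**The concern.** Stability is a claim that little or nothing was lost. A test whose null is zero change is built to find a difference, so its significant result is evidence that scores moved. Making p<0.05 the pass mark for a stability claim therefore asks the wrong question of the data. A K/N group that held its Week 2 gain exactly would nearly always fail the step, and a rule based on change from baseline could pass a group that had lost much of its gain.

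A within-group statement intended for labelling depends on this step. In addition, 13.8.3 places a further C-SSRS hypothesis after this one and says that testing continues only while significance is reached, whereas 13.9 ends at step 5. If the longer list governs, a step that stable patients almost never pass would stand in front of that hypothesis.

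**Working it through.** **Inputs.** From Table 15: two-sided alpha 0.05, N=56 and N=28, effect sizes 0.441, 0.636, 0.267 and 0.384. From 13.8.3: 56 evaluable K/N subjects. Effects are in SDs of the tested change; the documents do not give that SD in scale points.

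**Reproducing Table 15.** For a one-sample t-test, power = P(|T| > t(0.975, N−1)), with T non-central t on N−1 df and non-centrality d√N. The critical values are 2.004 (N=56) and 2.052 (N=28).

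| N | d | d√N | Power computed | Table 15 |
|---|---|---|---|---|
| 56 | 0.441 | 3.300 | 0.900 | 90% |
| 28 | 0.636 | 3.365 | 0.900 | 90% |
| 56 | 0.267 | 1.998 | 0.501 | 50% |
| 28 | 0.384 | 2.032 | 0.500 | 50% |

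All four columns reproduce. Table 15 is an ordinary test for a non-zero change.

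**Reading 1: change from Week 2 to end of study.** With true change 0, P(p<0.05) = 0.050 at either N. A simulation of 200,000 trials at N=56 gave 0.0502: 0.0250 significant worsening and 0.0252 significant further improvement. Significance needs an observed shift of 2.004/√56 = 0.268 SD. A stable group passes 5% of the time, or about 2.5% if only the favourable direction counts. Significant further improvement would rule out loss, but it demands more than the hypothesis claims. An MMRM contrast tested against zero behaves in the same way.

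**Reading 2: change from baseline.** The documents give no expected improvement, so assume a Week 2 gain of 0.8, 1.0 or 1.2 SD with half then lost. The remaining 0.4, 0.5 or 0.6 SD still gives p<0.05 with probability 0.837, 0.957 or 0.993 at N=56. With fewer subjects the rate falls: for 0.5 SD it is 0.808 at an assumed n=34 and 0.650 at n=24. At every one of these values, a group that lost half its gain would usually pass.

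**Reading 3: non-significance counts as stable.** This reverses the rule in 13.9. At N=56 a true worsening of 0.267 SD would be called stable with probability 1 − 0.501 = 0.499, and one of 0.441 SD with probability 1 − 0.900 = 0.100. A smaller or noisier sample would make the claim easier.

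**A rule that does test stability.** Let M be the largest acceptable worsening. Claim stability if the upper limit of the two-sided 95% CI for worsening is below M. At true change 0, power = P(T > t(0.975, N−1)) with non-centrality M√N.

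| Margin M (SD), N=56 | 0.2 | 0.3 | 0.381 | 0.4 | 0.441 | 0.5 |
|---|---|---|---|---|---|---|
| Power | 0.312 | 0.597 | 0.800 | 0.837 | 0.900 | 0.957 |

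Fewer contributors need a wider margin. Section 13.8.3 assumes 30% K/N relapse in the text and 52% relapse-free in the 90%-power column of Table 12, and relapsed subjects are withdrawn (8.1). If only relapse-free subjects counted, n would be 56 × 0.70 = 39 or 56 × 0.52 = 29, and the margin for 80% power would be 0.46 or 0.54 SD. These counts are illustrative; an MMRM also uses the earlier visits of withdrawn subjects.

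**The case against.** The strongest reply is that 13.9 fixes a significance level, not a null hypothesis. A no-worsening test against a margin also yields a p-value, so a margin named in the analysis plan promised before enrolment (6.4) could satisfy the p<0.05 rule. That is correct. A reader might infer that no p<0.05 rule could ever support step 5, and the documents do not support that. The defect is the zero-change null together with the missing margin.

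A second reply is that Table 15 is only a sample-size table, tied to step 5 by position. Two of its columns use N=28, the size of a comparator arm, so it may be a general aid for within-group tests. The link is indeed not explicit. But the table directly follows the hypothesis, its one-group form fits, and N=56 is the K/N count. If it is set aside, step 5 has no stated null at all.

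A reader might also infer that the rule rewards deterioration, since at N=56 a true worsening of 0.2 SD gives p<0.05 31% of the time and one of 0.4 SD gives it 84% of the time. Those are correct rejection rates, but counting them as passes assumes that significant worsening would be claimed as success. Section 13.4.2 frames the secondary hypotheses as favouring K/N, and with that direction worsening would almost never pass.

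Finally, it is tempting to take K/N retention from Table 14 ("K/N success rate p_2 at Week 6") to price a margin. The 0.6 there does not fit its own row: ln(0.225)/ln(0.6) = 2.92, against a printed hazard ratio of 3.89. The 0.43 is a threshold for reaching significance, not planned retention. Neither is used here as a forecast.

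**Conclusion.** The point holds. As written, step 5 pairs a stability claim with a two-sided p<0.05 requirement and a no-change null, and states no margin. None of the three readings of that test supports the claim. The 5% figure (2.5% directional) is exact for a t-test under the assumption that the change runs from Week 2 and is truly zero; the plan does not fix that starting point. The baseline-reading figures rest on assumed effect sizes and, like the retained-subject margins, are illustrations.

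The reach is small. In 13.9 step 5 comes last, is tested only if steps 1 to 4 succeed, and blocks nothing listed there. A reader should not infer any damage to the primary result or to error control for steps 1 to 4. At stake is one within-group labelling statement, plus the C-SSRS hypothesis if the order in 13.8.3 is the one intended. The plan should be corrected, but the design is not in question.

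**What to change.** In 13.9, specify for step 5 the instrument, the end visit (Day 42, if that is what is meant) and the K/N Day 14 to end-visit contrast from the planned MMRM. State a margin for acceptable worsening and justify it in scale points. Claim stability only if the upper limit of the two-sided 95% CI for worsening is below that margin. The 0.05 level need not change. Replace Table 15 with the power for the margin; its first column already equals the power for a 0.441 SD margin at N=56 with true change 0.

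If no margin can be justified, take step 5 out of the p<0.05 sequence and report the Week 2 to end-visit change with its 95% CI.

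In either case, make 13.8.3 and 13.9 list the same steps in the same order, and say whether the C-SSRS follow-up hypothesis belongs to the sequence.

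The cost is wording and one margin, with no new assessments. The price of the margin rule is power: a margin tighter than about 0.38 SD gives less than 80% power even with all 56 subjects. The alternative costs one within-group labelling claim.
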